consent process may take place at one of the following locations: (1) the VAPSHCS Seattle Campus; (2) VAPSHCS American Lake Campus or (3) IBIC at the UW.

The consent process will occur at a time deemed mutually feasible for the Veteran and staff member and coordinated on a case-by-case basis. The consent process will take place in a private location (e.g., a medical exam room or private conference room).

A research staff member will review each section of the informed consent form (ICF) approved by all regulatory institutions, inviting discussion to ensure comprehension.

Staff will be trained by study investigators to ensure competency to discuss informed consent and strategies to ensure there is no coercion.

Participants will be provided with as much time as needed to review the ICF and ask the research staff member questions about the ICF, their rights as human participants, and participation in the study. Potential participants will be fully informed of all risks and benefits prior to giving their written informed consent and prior to enrollment in the study.

If during the course of this contact the potential participant has questions that cannot be addressed by research staff, one of the study investigators or the research manager (depending on the nature of the questions) will follow up with the potential participant to answer the questions. Participants may take time to think about participating and render a decision in a subsequent visit.

Potential participants will be asked to repeat back understanding of this material as necessary. Individuals will not be permitted to participate if there is any question as to whether a person is able to provide informed consent.

The participant will then be asked to sign and date the ICF. Research staff will also date and sign the ICF. All participants will be offered a copy of the signed ICF for their records. A scanned copy of the consent form and an enrollment note template will be sent to the VAPSHCS Research Compliance Officer (RCO) as per VAPSHCS guidelines. In addition, a note of enrollment will be made in CPRS.

Research staff will also review a HIPAA authorization form with the participant that permits research staff to review in CPRS encounters of providers running the treatment groups to confirm attendance of said groups and extract data collected during treatment.

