Assignment to one of the 3 groups will be accomplished with a Microsoft Excel spreadsheet with random numbers created by the research manager with the guidance of the biostatistician. Only a research staff member who does not have access to study data during subject enrollment will conduct the randomization procedures. This randomization assignment will be entered into a password-protected database located on a VA secure drive. Research staff will complete a randomization case report form for each randomized subject that will be filed with study data.

The staff randomizing subjects will convey assignment to [name] via email with only a code number used i.e. no identifying information to identify the participant. [name] will then update the master list of participants, both research and non-research, of the clinic portion of the program.

Subjects will be sent a letter that outlines the schedule of treatment sessions they will attend.

Research staff will re-screen participants on approved mutable eligibility criteria (e.g. pain intensity, frequency, etc.) if 6 months or more has elapsed between the consent process and randomization.

Randomization may take place up to four weeks prior to the start of the treatment groups for that particular cohort.

D6m. Treatment Scheduling: Research and Non-Research Participants

Cohorts of study treatment groups will be offered beginning every four months. In each 4-month period, there will be two class options for each condition, one based in Seattle and one at American Lake. Thus, there will be six classes offered per four month period, or a total of 18 classes per year.

Trained instructors will commit to offering three groups per year: one of each treatment type. This will reduce the potential for therapist bias in on the outcomes. Up to 15 participants can be enrolled in each group treatment class.

[name] will maintain lists of group assignments (for both research and non-research participants) and coordinate the scheduling of group class appointments. Both [name] and the unblinded research staff member responsible for randomization will have access to this information and be available to provide back-up if [name] is absent or preoccupied.

As aforementioned, the research staff conducting randomization procedures will alert [name] that a research participant has been randomized.

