Participation in less than 4 treatment sessions will be considered a protocol deviation. A Note-to-file will be drafted at the end of each cohort to report research participants that completed less than 4 treatment sessions.

Data Collected during Treatment Sessions

Participants will complete and hand in a form regarding their completion of tasks or "homework" assigned by the clinician from the previous session.

In addition, participants will complete and hand in forms before and after each session that include questions regarding pain intensity and comfort level, as well as questions about what the participants have found helpful or non-helpful about the treatment.

Finally, study clinicians will complete a form each session that captures information regarding the perceived engagement of each participant in that particular session. All of these forms will be labeled with a subject's name.

Information will be gathered during the group interventions as per standard of care procedures that all attendees will do regardless of their participation in the study. The clinicians running the groups will not have access to the crosswalk between study data and participants' identities.

Following each session, per usual care the clinician will enter a progress note in CPRS for each participant, indicating attendance or absence for that particular session. The note will also include the length of the group session, as well as basic content covered during the session.

Information gathered during the group sessions (e.g., homework logs, pre- and post-class pain ratings, patient engagement) will be used for clinical supervision and treatment planning. This clinical information will be scanned and stored on a secure drive (PUG_Services (<\\RO1PUGHSM03.r01.med.va.gov\RCS>)\Psychology\SKILLS CLINICAL GROUPS) within the Rehabilitation Care Service. Access to this drive will be limited to clinicians who are running the classes and their clinical supervisor, and unblinded staff members.

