Unblinded staff members will extract these data associated with the main RCT as well as with the open-label phase (since all group participants will be completing the forms regardless of study status). These staff members will have access to this secure limited-access drive, and to the cross walk linking names/study IDs. These two staff members would identify the veterans who are study subjects and access the PDFs of the scanned information in this clinical drive, and enter the data directly into a secure database with the participant's code number (study id).

In this way, we leverage existing clinical data to address an important scientific question (i.e., whether engagement in homework and experience within sessions is associated with outcomes), but none of the clinicians are engaged in research activities, and there is no additional burden to the subjects.

The staff member will enter the data labeled with only the participant's code number into a password-protected database separate from all non-treatment study data. The staff member will not enter the data collected from non-research participants.

Audio Recordings

All group treatment sessions will be audio recorded to ensure compliance to treatment procedures. A portion of treatment sessions will be randomly selected to be reviewed by study researchers to ascertain fidelity to protocol. Study clinicians will receive feedback as needed if they diverge from protocol.

The study clinicians will notify participants before the start of the session that s/he will be recording the session, and all participants in the group (including non-research participants) will be asked to complete requisite consent forms to record voice. The audio recordings will be collected using a VA approved encrypted device.

The recordings will be stored on a secure server at the VA (V:\Chronic Pain Skills group\Fidelity Recordings). Audio recordings will only be reviewed by study personnel and used for assessing consistency between study clinicians. The audio recordings will not be labeled with any identifying information.

The only identifying information that will be contained within the recordings will be participants' voices and if the study clinician or group members state participants' names during the discussion.

Treatment Intervention Discontinuation

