Post-Treatment Telephone Assessment Period	Up to 4 telephone assessments conducted within a one-week period	Once following end of treatment	About 45-60 minutes total	\$25
Post-Treatment Brain Activity Assessment	One in-person assessment at the UW Integrated Brain Imaging Center (IBIC) at the UW	Once following end of treatment	About 45-60 minutes	\$100

Post-Treatment Sleep Sub-Study Procedures	Wear actigraph on wrist, complete sleep/wake diary twice a day, call in wake/bedtimes twice in a day during a one-week period	Once following end of treatment	2 hours for sleep/wake diary, continuous for actigraph device	\$40
3 Month Telephone Assessments	Up to 4 telephone assessments conducted within a one-week period	Three months following end of treatment	About 45-60 minutes total	\$25
3 Month Sleep Sub-Study Procedures	Wear actigraph on wrist, complete sleep/wake diary twice a day, call in wake/bedtimes twice in a day during a one-week period	Three months following end of treatment	2 hours for sleep/wake diary, continuous for actigraph device	\$40, plus \$15-30 bonus as applicable
6 Month Telephone Assessments	Up to 4 telephone assessments conducted within a one-week period	Six months following end of treatment	About 45-60 minutes total	\$25
Bonus Payment: All telephone assessments completed	All seven telephone assessment periods are completed	Over 9-month period (see timeline listed above)	Totaling about 5-7 hours total over a 9-month period	\$50
Open Label Phase Study (cohorts 1-9)	Two telephone assessments, 8 treatment sessions	Following completion of the main phase of the study	About 13 hours over a 3-month period (assessments and treatment sessions included)	\$10 per assessment completed

D6t. Study Data

Main Study:

The following is a list and description of the data measures included in the study. We list the demographic and descriptive information we propose to collect from the study participants in the next paragraph. The primary outcome, secondary outcome, covariates (variables to control for in planned analyses if needed), and mechanism (mediator and moderator) variables for this study are listed in Table 4 (page 33). Details regarding a subset of the key measures are provided below. All outcome measures will be administered by research staff members blind to group allocation.

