Research staff will record all SAEs using a standard form that records the subject’s code number, date of SAE, severity, attribution level to study, action taken and outcome. These adverse events will be provided annually in this format to the DSMC, both the VAPSHCS and UW IRBs and NCCIH in accordance with requirements.

The Chair of the DSMC will be contacted when an SAE is discovered to receive consultation on the matter. The Chair of the DSMC will use her discretion to determine whether the other DSMC members should also provide additional consultation.

3f. Data Quality Assurance and Monitoring

Description of Plan for Data Quality and Management

The research manager and study staff will review all data collection forms on an ongoing basis for data completeness and accuracy as well as protocol compliance. Data verification will take place in the form of double-data entry. Specifically, two separate study staff members will enter data from the hard copy forms into the database to ensure accuracy of data entry. Visual Basic for Applications (VBA) code inserted in the Microsoft Access database will verify the 2nd entry against the 1st entry. Any discrepancies between the two entries will cause a warning window to open informing the data operator that a discrepancy has been detected.

All data entry discrepancies between these two data entries will be solved by the staff member completing the 2nd portion of double entry.

Exploratory data collected during the treatment sessions will be singly entered into the Treatment Database. For quality control, a second unblinded staff member will review 10% of the treatment data at the completion of the study. If there is more than a 5% error rate, then Investigators will be notified to determine a plan of action which may include implementing a 2nd entry verification.

All group treatment sessions will be audio recorded to ensure compliance to treatment procedures. A portion of treatment sessions will be randomly selected to be reviewed by study researchers to ascertain fidelity to protocol. Study clinicians will receive feedback as needed if they diverge from protocol.

In addition, research study staff will review the study data in detail on a quarterly basis to detect any systematic issues with data collection.

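### The randomization form is filed with the study data that staff review, and no stated safeguard keeps it from blinded outcome assessors

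*Combined protocol and SAP*

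**What the plan says.** **Blinding commitment.** D6t (Study Data): "All outcome measures will be administered by research staff members blind to group allocation". The Blinded/Unblinded Research Staff table in D6v lists those who collect outcome data as blinded during data collection. It also lists those who help manage outcome data as blinded.

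**Allocation records.** D6l (Randomization) restricts who randomizes: "Only a research staff member who does not have access to study data during subject enrollment will conduct the randomization procedures". It protects the electronic record: "This randomization assignment will be entered into a password-protected database located on a VA secure drive". For the paper form it says only: "Research staff will complete a randomization case report form for each randomized subject that will be filed with study data".

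**Form review.** Section 3f: "The research manager and study staff will review all data collection forms on an ongoing basis".

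**Treatment records.** D6n limits attendance records and scanned session forms to clinicians, named persons and unblinded staff. Unblinded staff extract the session data into a "password-protected database separate from all non-treatment study data". D6o sends withdrawal data to the unblinded treatment database.

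**Medical record.** After each session the clinician writes a CPRS note on attendance. D6n adds: "The note will also include the length of the group session, as well as basic content covered during the session". The HIPAA authorization in D6d "permits research staff to review in CPRS encounters of providers running the treatment groups to confirm attendance of said groups", and to extract treatment data. D6t says that health care visits can be verified in the medical record, without saying by whom.

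**The concern.** The primary outcome is a 0-10 pain rating spoken to a telephone interviewer by a participant who knows which class he or she attends. Participant blinding is not available, so keeping the interviewer unaware of the arm is the main remaining protection against differences in prompting, tone or probing.

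The plan recognises this hazard and separates most treatment records from blinded staff. The record that states the allocation most directly is instead filed with the general study data. If a blinded collector or data manager handles that file before the post-treatment ratings, the commitment in D6t fails for that participant, and nothing in the plan would prevent or record it.

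**Working it through.** No figure in the plan depends on this point, so the main check sets the provisions side by side.

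| Record | Stated access limit | Where |
|---|---|---|
| Electronic assignment | Password-protected database; users not named | D6l |
| Group lists | Named coordinator and unblinded randomizer | D6m |
| Attendance records | Named persons and unblinded randomizer | D6n |
| Scanned session forms | Clinicians, supervisor, unblinded staff | D6n |
| Extracted session data | Entered by unblinded staff; separate database | D6n |
| Open-ended modality feedback | Collected by unblinded staff | D6k |
| Open-label scheduling | Done by unblinded staff | D6r |
| **Randomization form** | **None; filed with study data** | D6l |
| **CPRS session notes** | **None specific to blinded staff** | D6d, D6n |

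1. *Is filing with study data a location?* Yes. D6d uses the same phrase for the enrollment form and contrasts it with the consent and HIPAA forms, which are kept elsewhere. D6v stores hard-copy data in locked cabinets and rooms and mentions no separate allocation file.
2. *Who reaches that location?* Section 3f names the research manager and study staff without excluding blinded staff.
3. *Does another rule in D6l cover the paper form?* No. The password protects the electronic record. The rule on the randomizer limits what the randomizer sees of study data, not what assessors see of the allocation.
4. *Does the form show the arm?* Its contents are not given. That it does is an inference from its purpose.
5. *CPRS.* Notes on content covered would distinguish hypnosis, meditation and education. The D6d permission names research staff in general, and the D6t visit verification names nobody.

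**Illustration of stakes.** The shift and the exposure rate below are assumptions. Take D6z's 80 per arm and its largest SD, 1, with no true effect and a spurious mean shift *b* in both HYP and MM. The noncentrality is λ = 80 × (2/3) × *b*² / 1², and the omnibus F test has 2 and 237 degrees of freedom (critical value 3.03 at 5%).

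| Shift per affected participant | Share of HYP and MM participants affected | *b* | λ | Rejection rate |
|---|---|---|---|---|
| 0.1 | all | 0.1 | 0.533 | 9.2% |
| 0.2 | all | 0.2 | 2.133 | 23.6% |
| 0.1 | one quarter | 0.025 | 0.033 | 5.2% |
| 0.2 | one quarter | 0.05 | 0.133 | 6.0% |

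For scale, the smallest contrasts assumed in D6z are 0.6 − 0.3 = 0.3 (MM minus ED) and 0.8 − 0.3 = 0.5 (HYP minus ED).

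**The case against.** The strongest reply is that the plan has a consistent role-based scheme, and that silence about one form is not a breach of it. Unblinded staff handle attendance, session data, modality feedback and open-label scheduling. Section 3f speaks of data collection forms, while Table 1 describes randomization as a step at which no data are collected, so the form may fall outside that review. D6v assigns data entry to study support persons, who need not be assessors. Scripted questions and a response key limit what an interviewer could influence, and section 3j says charts will not be monitored for adverse events, which removes one reason for assessors to open CPRS.

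Much of this stands, and it rules out three stronger readings that a reader might infer:

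- *Assessors see the arm, or blinding is defeated.* No provision shows an assessor opening the form or a session note.
- *CPRS appointments reveal the arm.* D6n says only that sessions appear among regular appointments, and D6a places all three treatments in one program. Nothing says that the appointment title names the class.
- *The type I error is inflated to 9% or 24%.* Those figures need a shift in the same direction averaged over every HYP and MM participant. The documents give neither a shift nor an exposure rate.

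The reply does not reach the filing rule itself. That is a stated instruction rather than an omission, and none of the listed safeguards covers the form. The CPRS point is weaker, because D6n already gives extraction to unblinded staff. It amounts to a loosely worded permission.

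**Conclusion.** The concern holds as a risk to blinding. D6l places the allocation form among data that section 3f opens to the research manager and study staff, while D6t and the D6v table require outcome collectors and outcome-data managers to be blind. The conclusion assumes that the form records the arm and that blinded staff use the same files. The first is very likely and the second plausible, but neither is documented. Unblinding is not shown to have occurred.

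The size of any bias cannot be derived from the documents. The illustrative error rates run from about 5% to 24%, depending entirely on the assumed shift and exposure. The CPRS wording is a secondary gap. The point merits correction because it touches the primary outcome and is cheap to close.

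**What to change.** - **D6l:** keep the randomization form, on paper and electronically, only in the access-restricted unblinded treatment file or database until at least the participant's 6-month assessment is complete. Say who may open it.
- **D6d and D6t:** after randomization, limit review of treatment encounters and verification of visits in CPRS to the existing unblinded staff.

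The cost is protocol wording and a change of filing location, using staff and storage that the plan already has. If follow-up is over when this is acted on, the trial report should state where the forms were held and which staff had access to them.
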